## 1.5 Risks and Benefits

### Risks

In general, acetazolamide is considered a safe drug. Per the package insert, severe adverse reactions that have been reported with administration of acetazolamide include seizures, muscle paralysis, hepatic necrosis, hepatic failure, hepatic encephalopathy, toxic epidermal necrosis, agranulocytosis, anaphylaxis, aplastic anemia, hemolytic anemia, Stevens-Johnson syndrome, pancytopenia, acute generalized exanthematous pustulosis, renal failure, and renal tubular obstruction. The incidence of each reaction is unknown. It is likely that individuals who have significant baseline allergy to acetazolamide and other components, hepatic dysfunction, blood dyscrasias, and/or renal dysfunction would be at higher risk for these severe reactions. Thus we are assessing for hepatic dysfunction, renal dysfunction, allergy, and blood dyscrasias at baseline and excluding individuals with significant disturbances in their laboratory assessments or have a history of allergy to the components of the therapeutic agent or placebo (as defined by the exclusion criteria below). We will monitor complete blood count (CBC), liver function tests (LFT), venous blood gas (VBG or bicarbonate/CO2), electrolytes, and creatinine, and urinalysis with urine creatinine, calcium, and protein at baseline and regularly throughout the study, and if any individual meets exclusion criteria at any point during the study, we will terminate their treatment. Patients may develop acidosis on acetazolamide therapy, which may lead to inability to continue the therapy longer or a decrease in dosage. Acetazolamide has been associated with growth suppression in pediatric patients, although not all individuals have been reported to have poor growth and the dosages associated with growth suppression have not been consistent. Growth has been reported to resume and improve after discontinuation of acetazolamide. We will monitor growth parameters (height, weight, head circumference) regularly throughout the study and tailor their management and continuation in the study on a case by case basis. We will monitor patients' acid/base status and titrate acetazolamide accordingly. We will also obtain a one-time measurement of acetazolamide serum concentration at steady state at the six-month visit.

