#### **3.2 Number of Subjects**

We aim to enroll 26 evaluable patients. Up to 7 additional patients will be enrolled to account for a 20% loss in sample size due to ineligibility, major treatment violation, cancellation, or withdrawal prior to completion of the 6-month blinded phase of the study. Maximum projected accrual is, therefore, 33 patients. Enrollment will continue until the 26th evaluable patient completes the blinded phase. Enroll will pause when 26 patients have either completed or are

actively completing the blinded phase; enrollment will reopen if any of these patients withdraw before completing the blinded phase.

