## 6.2 Visit 2 (Remote)– Week 2-3

- Procedural elements
  - Blood collection (CBC, electrolytes and/or VBG, liver function tests, kidney function tests)
  - Urine collection (same as section 6.1)
- Medication adherence questionnaire (appendix E): family to send this to us electronically or via mail.
- Interview elements
  - AE assessment
  - Concomitant medication review
  - Ongoing therapies (same as section 6.1)
- Dose Adjustment (see section 5.2) – After venous blood gas and electrolytes have resulted, partnering clinician will instruct patient/caregiver regarding administration of drug or placebo via phone call, telehealth, or in person.

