### 7.2 Statistical Methods

#### Descriptive Statistics

Univariate descriptive statistics and frequency distributions will be calculated, as appropriate for all variables. Baseline values for demographic, clinical, and outcome variables (primary and secondary) will be tabulated for the treatment groups. These analyses will help identify potential confounding variables to be used as covariates in sensitivity analyses. Distributions across subgroups used in randomization will be qualitatively compared to assess whether the randomization was successful in equalizing distributions of these prognostic variables across treatment groups. Putative prognostic variables that will be investigated through these descriptive analyses include variables such as sex, baseline Mini-ICARS score, age, and baseline NPCRS score.

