### **Secondary Endpoint Analysis Approach:**

**Secondary Endpoint 1:** Incidence of (a) drug related adverse event(s) and (b) drug related serious adverse event(s) while they are on blinded therapy. The maximum grade for each type of adverse event will be summarized using the CTCAE v5.0. Using the safety set (see Section 7.3), the frequency and percentage of patients with a grade 1+ adverse event or serious adverse event classified as possibly, probably, or definitely related to the study treatment will be summarized by treatment arm. The frequency and percentage of patients who discontinue study treatment due to adverse events will also be reported by treatment arm. This analysis will be repeated to evaluate incidence of (a) drug related adverse event(s) and (b) drug related serious adverse event(s) for the duration that patients remain in the open label extension.

**Secondary Endpoint 2:** PMM2-Biomarker and other scores including:

- carbohydrate deficient transferrin results (Mono/Di, A/Di, Apo CIII1/Apo C III2, Apo CIII0/Apo CIII2),
- electrolytes (Na, K, Cl, CO2),
- VBG (pH, pCO2, PO2, CO2, Base excess) or bicarbonate/CO2,
- liver function tests (AST, ALT, GGT, indirect and direct bilirubin, total protein, albumin, alkaline phosphatase),
- kidney function tests (BUN, Creatinine, Urinalysis, urine calcium/creatinine ratio, urine protein/creatinine ratio),
- growth (height, weight, head circumference),
- vital signs (blood pressure, respiratory rate, heart rate),
- PROMIS scores,
- the PATA score,
- and NPCRS score.

As these endpoints are all numeric, and to identify if the post blinded therapy or final measurement of the open label extension is different from the baseline value, we will use a linear regression model to test if there is a change from baseline. Using the full analysis set (see Section 7.3), the between-arm mean difference in 6-month scores will be evaluated via a linear regression model predicting 6-month scores from baseline scores and treatment arm. This analysis will be repeated based on the final measurement of the open label extension. A nominal significance level of  $\alpha=0.05$  will be used for all analyses.

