## 7.3 Subject Populations for Analysis

- *Intent-to-treat set*: All randomized patients, regardless of whether they received their assigned study treatment.
- *Full analysis set*: All randomized patients who complete the baseline and 6-month visits.
- *Safety set*: All randomized patients who receive at least one dose of acetazolamide or placebo.
- *Per-protocol set*: All randomized patients who report taking at least 4 weeks of their assigned study treatment and complete the baseline and 6-month visits.

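### Section 1.5 relies on the exclusion criteria to guard against blood dyscrasias, but section 4.2 and the laboratory rules contain no blood-count criterion; CBC is also the one remote-visit panel with no by-arm comparison

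*Combined protocol and SAP*

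**What the plan says.** **The risk.** Section 1.2 reports occasional bone marrow suppression and blood dyscrasias with acetazolamide. Section 1.5 lists agranulocytosis, aplastic anemia, hemolytic anemia and pancytopenia among the severe reactions. It gives their incidence as unknown and considers patients with existing blood dyscrasias likely to be at higher risk.

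**The safeguard.** Section 1.5 answers this risk by assessing for "blood dyscrasias at baseline and excluding individuals with significant disturbances in their laboratory assessments", with the limits set "as defined by the exclusion criteria below". It adds that treatment will end for anyone who meets an exclusion criterion on study.

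**The data.** A CBC with differential is collected (section 3.7). The remote-visit draw in section 6.2 is "Blood collection (CBC, electrolytes and/or VBG, liver function tests, kidney function tests"; sections 6.3 and 6.4 repeat it. Visits 1 and 5 use the fuller panel in 6.1, which also includes CBC.

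**The analysis.** Section 7.2 opens with a general statement: "Univariate descriptive statistics and frequency distributions will be calculated, as appropriate for all variables". It states by-arm tabulation for baseline values. Under Secondary Endpoint 1, "The maximum grade for each type of adverse event will be summarized using the CTCAE v5.0", and patients with a grade 1 or higher event "classified as possibly, probably, or definitely related to the study treatment will be summarized by treatment arm". Secondary Endpoint 2 compares electrolytes, blood gas, liver tests and kidney tests between arms. CBC is not on that list, nor among the secondary endpoints in section 3.5.

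**The concern.** A reader of section 1.5 would conclude that a patient with significant cytopenia cannot enter the trial, and that one who develops it comes off drug by rule. Both protections depend on section 4.2 containing something to apply. If it does not, the risk section describes a protection that is absent, in a placebo-controlled trial that enrolls children from age 4.

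The second matter is smaller. Objective 2 is to evaluate adverse events of longer-term use. CBC is drawn repeatedly for a named hazard, yet it is the panel for which no by-arm summary of on-treatment values is stated. A non-serious fall in neutrophils, platelets or hemoglobin would then appear by arm only if someone records it as an adverse event.

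**Working it through.** The point rests on no figure in the plan. The check sets the provisions side by side.

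1. **Exclusion criteria (4.2).** There are 5 based on blood chemistry or acid-base status (hepatic, renal, hypokalemia, hyponatremia, hyperchloremic acidosis), 1 for adrenal insufficiency, 2 for hypersensitivity, and 5 others (recent experimental drug, prohibited medicines, another trial, pregnancy or nursing, weight). That is 5 + 1 + 2 + 5 = 13. Criteria on hemoglobin, white cells, neutrophils or platelets: 0. The 11-item list in the Study Summary has none either.

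2. **Laboratory rules on study.** The list in 8.1 of laboratory values to be recorded as adverse events, with its drug stop, has a hepatic and a renal entry. The laboratory part of 8.5 has the same two. Section 4.3 refers back to 8.1. Blood-count entries: 0.

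3. **Consequence for 1.5.** The exclusion and the treatment end both act through 4.2. With no blood-count criterion there, neither can be triggered by a blood count, whatever its value.

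4. **What remains on study.**
   - Section 8 asks for thrombocytopenia monitoring within 4 weeks of a dose increase, and for the principal investigator to reconsider risk after significant changes in blood tests.
   - Sections 6.4 and 6.8 repeat the CBC after a dose change at Visits 4 and 8.
   - Section 8.6 sends SAEs to the DSMB.
   - None of these states a blood-count threshold, and none governs entry.

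5. **By-arm comparison of remote-visit panels.** Four panels are drawn: CBC, electrolytes and/or blood gas, liver, kidney. Secondary Endpoint 2 covers 3 of the 4, all but CBC.

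6. **Would adding CBC to Secondary Endpoint 2 be enough?** The blinded phase has 4 scheduled post-baseline CBCs per patient (Visits 2, 3, 4 and 5), or 26 × 4 = 104 at the target of 26. The blinded-phase regression uses the 6-month value only, so Visits 2 to 4, 26 × 3 = 78 of the 104, would go unused. It also runs on the full analysis set, "All randomized patients who complete the baseline and 6-month visits". A patient who stops early and has no 6-month visit is therefore left out, although the early-termination visit (6.10) draws the 6.1 panel with CBC. These counts show how much collected data a table would use. They do not show that any planned result is wrong.

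**The case against.** The strongest reply is that blood counts are already covered on study. Agranulocytosis or aplastic anemia would probably meet a seriousness criterion and reach the DSMB. Section 3.7 defines adverse events by CTCAE version 5, so a gradeable fall is arguably an adverse event already and would be counted by arm at grade 1 or above. Descriptive statistics are promised for all variables. The maximum-grade summary sits in a paragraph whose other summaries are by arm, so reading it as pooled is strained.

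Much of this stands against the analysis part. A reader might infer that attribution would filter out blood-count changes. Table 5 does not support that: an event is unrelated only if this can be determined with certainty, and a previously known toxicity points toward a definite relationship. A reader might also infer that hematologic toxicity goes unmonitored. The provisions in section 8 and the repeated CBCs contradict that.

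What survives is narrower. Section 8.2 leaves laboratory events to a judgment of clinical significance, which sits uneasily with section 3.7. Appendix D might settle this, but it is not in the text available. The general descriptive sentence names neither arm nor on-treatment values.

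None of the reply touches the safeguard. Adverse event grading, investigator review and SAE reporting all act after randomization and cannot supply the missing entry criterion. The review in section 8 is discretionary, whereas 1.5 describes a rule.

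**Conclusion.** The concern holds, chiefly as a gap in the safeguard. Section 1.5 promises exclusion and treatment end for a risk on which 0 of 13 criteria in 4.2 and neither laboratory list (8.1, 8.5) has an entry. As written, a patient with marked cytopenia at Visit 1 could be randomized, and the treatment end in 1.5 could not be triggered by a blood count.

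The analysis gap is secondary and descriptive: 1 of 4 remote-visit panels lacks a by-arm comparison. It matters for non-serious falls that are not logged as adverse events. The documents do not show that any estimate, error rate or decision would change, and the primary analysis is unaffected.

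The conclusion assumes that the list in 4.2 is complete. Hematology grades in Appendix D would narrow the analysis part, but a grading scale supplies neither an exclusion criterion nor a by-arm table of values. The change is worth making because it is cheap and concerns a risk the protocol itself names.

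**What to change.** **Main change, section 4.2.** Add: 'Hemoglobin, neutrophil count or platelet count at or beyond CTCAE v5.0 grade [set by the clinical team] at Visit 1.' The Visit 1 CBC is already drawn before randomization, and neutrophils follow from WBC and the differential. Through 1.5 the same criterion will end treatment on study, so the grade should be high enough to catch only clinically important cytopenia. A low threshold would take patients off drug for minor changes and, under the treatment policy strategy, could dilute the primary effect. The cost is an occasional exclusion or treatment stop.

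Simply rewording 1.5 to match 4.2 is not recommended. It would make the text consistent by removing a protection.

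**Secondary change, section 7.2, Secondary Endpoint 1.** Add: 'Using the safety set, worst post-baseline CTCAE v5.0 grade and shift from baseline grade for hemoglobin, WBC, neutrophils and platelets will be tabulated by treatment arm for the blinded phase, from all post-baseline CBCs, scheduled or repeat, whether or not an adverse event was logged.' The table is descriptive, with no test. The cost is one more table from data already collected; no visit, assay or sample size changes.

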## Study Summary

Title	A randomized, double-blind, placebo-controlled study evaluating Acetazolamide efficacy in ataxia in PMM2-CDG
Running Title	Acetazolamide Trial in PMM2-CDG
Protocol Number	20-000634
Methodology	Randomized, double-blind, placebo-controlled, parallel
Overall Study Duration	1 years (52 weeks)
Subject Participation Duration	Treatment period = 6 months (26 weeks); Open Label period = 6 additional months (26 weeks); Total of 1 year (52 weeks)
Single or Multi-Site	Multicenter – 3 sites (Seattle Children’s Hospital, Children’s Hospital of Philadelphia, Mayo Clinic)
Objectives	
Objective 1 (Primary): To determine the efficacy of acetazolamide in improving ataxia in patients with PMM2-CDG.
 
Objective 2 (Secondary): To evaluate for any adverse events related to longer term acetazolamide administration.
 
Objective 3 (Secondary): To examine the effect of acetazolamide on PMM2 biomarkers including carbohydrate deficient transferrin results, electrolytes (Na, K, Cl, CO2), VBG (pH, pCO2, PO2, CO2 excess) or bicarbonate/CO2, liver function tests (AST, ALT, GGT, indirect and direct bilirubin, total protein, albumin, alkaline phosphatase), kidney function tests (BUN, Creatinine, Urinalysis, urine calcium/creatinine ratio, urine protein/creatinine ratio), growth (height, weight, head circumference), vital signs (blood pressure, respiratory rate, heart rate), PROMIS scores, dysarthria using the PATA score, and NPCRS score.
 
Objective 4 (Secondary): To explore characteristics of individuals with PMM2-CDG who do not respond to acetazolamide.

Number of Subjects	26 total subjects

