### 3.3 Duration of Participation

The duration of participation is a maximum of approximately 1.75 years as outlined in Figure 1 below.

[figure not shown]

Figure 1. Study Timeline for visits 1 through 9

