### 3.6 Primary Safety Endpoints

The primary safety endpoint is incidence of (a) drug related adverse event(s) and (b) drug related serious adverse event(s) while patients are on blinded therapy as well as for the duration they remain in the open label extension.

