### 5.7.1 Blinding of Study

- Investigators, study staff in contact with patients, and subjects will be blinded. The research pharmacy will then dispense acetazolamide or placebo to the patient or study staff. Access to the randomization code will be strictly controlled by the research pharmacy and DMCC. Packaging, labeling, and appearance of the test and control treatments will be similar to maintain the blinding. Active drug concentrations will be prepared by the pharmacy prior to handoff to clinicians or patients/caretakers for administration. The study will proceed to open label continuation at Visit 5 (Week 40-56). During the study, the blind may be broken only in emergencies when knowledge of the patient's treatment group is necessary for further patient management. If the blind is broken for a subject, that individual will be removed from the blinded portion of the study. If a subject experiences an adverse event warranting unblinding procedures, the pharmacy will inform the physician of the prescribed treatment.

After all data are collected for the blinded portion of the study and all data cleaning is completed for these data, the data base for the blinded portion of the study will be locked and the study will be unblinded for analysis.

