### 6.5 Visit 5 – Week 21-34

- Interview elements:
  - Concomitant medication review
  - Ongoing therapies (same as section 6.1)
  - Medication adherence questionnaire (see section 6.2)
  - AE assessment
- Procedural elements:
  - Physical exam (see section 6.1)
  - Mini-ICARS
  - PATA
  - NPCRS
  - Blood collection (see section 6.1) In addition, random blood level of acetazolamide will be collected.

- Urine collection (see section 6.1)
- Survey given to families to complete and returned to site at or after visit by mail or electronically
  - PROMIS
- Open Label Extension (OLE) or discontinuation – investigator will discuss with family option of rolling over into an open label extension of the study where the patient will receive the drug. If patient/caregivers decide to proceed with OLE, the patient will be started on dose 1 of acetazolamide.

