## 6.9 Visit 9 – Week 49-105

- Interview elements:
  - Concomitant medication review
  - Ongoing therapies (see section 6.1)
  - \*Medication adherence questionnaire (see section 6.2)
  - AE assessment
  - Reason for discontinuation of study treatment and discontinuation of study
- Procedural elements:
  - Physical exam (see section 6.1)
  - Mini-ICARS
  - PATA
  - NPCRS
  - Blood collection (see section 6.1)
  - Urine collection (see section 6.1)
  - Annual screening ophthalmological exam including intraocular pressure testing.
- Survey given to families to complete and returned to site at or after visit by mail or electronically
  - PROMIS

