## 8 Safety and Adverse Events

Blood will be collected at regular intervals to assess electrolytes level, kidney function, coagulation factor, and measure of base. Urine will also be collected at regular intervals to assess calcium and protein levels. Routine urinalysis will also be performed to monitor for any significant changes in body fluids as a result of acetazolamide function. Monitoring for thrombocytopenia, electrolyte disturbances, and metabolic acidosis should be completed within 4 weeks of a dose increase. If significant changes occur in blood or urine tests, risk will be re-evaluated by the principal investigator to determine if acetazolamide should be continued as per below. The AE reporting period will encompass visits 0 to 9 of the study. If a subject withdraws early, we will attempt to assess AEs up to 91 weeks after enrollment through review of medical records.

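### The extension part of the primary safety endpoint is a crude percentage of patients with no exposure time, although Visit 5 to Visit 9 can span 15 to 84 weeks

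*Combined protocol and SAP*

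**What the plan says.** Section 3.6 defines the primary safety endpoint as the incidence of drug-related adverse events and drug-related serious adverse events "while patients are on blinded therapy as well as for the duration they remain in the open label extension". The only analysis of it is Secondary Endpoint 1 in section 7.2. That analysis gives the number and percentage of safety-set patients with a related event by arm, the maximum grade by event type, and discontinuations due to adverse events. The related-event analysis is then repeated "for the duration that patients remain in the open label extension". No time denominator, rate, time-to-event method, cut-off time or exposure summary appears.

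The timing of the phases is stated in several ways:

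- The Study Summary has "Open Label period = 6 additional months (26 weeks".
- The visit sections have "Visit 5 – Week 21-34" and "Visit 9 – Week 49-105", and Table 3 repeats both windows.
- Section 3.3 states: "The duration of participation is a maximum of approximately 1.75 years".
- Section 8 says of early withdrawals that "we will attempt to assess AEs up to 91 weeks after enrollment through review of medical records".
- Section 5.7.1 states: "The study will proceed to open label continuation at Visit 5 (Week 40-56".

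Section 3.1 lets a patient leave at any time after Visit 5. The safety set in section 7.3 is every randomised patient with at least one dose of either treatment, which includes patients who never enter the extension.

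**The concern.** Objective 2 asks about longer-term administration, and the extension is where most of the information beyond six months will come from. A percentage of patients with at least one event rises with time on drug even when the underlying risk is unchanged. If extension lengths differ widely, the figure cannot show whether a high value means more risk or more follow-up.

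The blinded and extension figures will come from the same table layout under one endpoint. A reader will naturally set them side by side, although the two phases can differ greatly in length. The denominator is also unsettled: carrying the safety set into the extension would count patients who took no extension drug and would dilute the percentage.

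**Working it through.** **The plan's own figures.** The documents state no adverse event rate, exposure time or safety precision, so there is no safety figure to reproduce. The one timing check that can be made agrees: 1.75 years × 52 = 91 weeks, the limit that section 8 uses for early withdrawals.

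**Inputs.** Visit 5 at weeks 21 to 34 (section 6.5); Visit 9 at weeks 49 to 105 (section 6.9); participation limit 91 weeks (section 3.3); therapy to start by week 1.5 (section 5.2). Event rates are assumptions.

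**Length of each phase, for patients who reach Visit 9**

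- Shortest extension: 49 − 34 = 15 weeks.
- Longest extension: 105 − 21 = 84 weeks, a ratio of 84/15 = 5.6.
- Longest under the 91-week limit: 91 − 21 = 70 weeks, a ratio of 70/15 = 4.7.
- Blinded exposure: 21 − 1.5 = 19.5 weeks to 34 − 0 = 34 weeks, a ratio of 1.7.

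Patients who leave early can have fewer than 15 extension weeks.

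**Effect on the percentage if the hazard is constant.** With λ first events per patient-year, the expected share with an event by T weeks is 1 − exp(−λT/52).

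| T (weeks) | λ = 0.5 | λ = 1 |
|---|---|---|
| 15 | 13% | 25% |
| 26 | 22% | 39% |
| 70 | 49% | 74% |
| 84 | 55% | 80% |

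A real cohort would mix lengths. If half the patients had 15 weeks and half had 70 (an illustration), λ = 1 gives (25% + 74%)/2, about 50%, against 39% if everyone had 26 weeks.

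**Effect if events cluster in titration.** Visits 6, 7 and 8 each follow the previous visit by 1 to 3 weeks, so titration ends at most 3 + 3 + 3 = 9 weeks after Visit 5. Suppose 30% of patients have a first event, on average at week 4.5, and none occur later. The crude figure is then 30% at either length. Time at risk per patient is 0.30 × 4.5 + 0.70 × T:

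- T = 15: 1.35 + 10.5 = 11.85 weeks, so 0.30/11.85 = 2.5 first events per 100 patient-weeks.
- T = 70: 1.35 + 49 = 50.35 weeks, so 0.30/50.35 = 0.6 per 100 patient-weeks.

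Here it is the rate, not the percentage, that depends on length. Neither measure is enough alone. Cumulative incidence at a fixed time avoids both problems.

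**Timing conflict.** With Visit 5 at weeks 40 to 56 as in section 5.7.1, the shortest extension would be 49 − 56 = −7 weeks, so that window cannot stand beside the Visit 9 window. A Visit 9 at week 105 also exceeds the 91-week limit by 14 weeks.

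**Precision.** If 5 of 26 patients had an event (19%), the exact 95% interval would be 6.6% to 39.4%.

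**The case against.** Four points can fairly be made for the plan.

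- **The extension is nominally 26 weeks, and 84 weeks is a corner of the windows.** This stands as far as it goes. The 84 weeks needs the earliest Visit 5 and the latest Visit 9, and it conflicts with the Study Summary and section 3.3. Yet 70 weeks remains possible under section 3.3, and section 8 itself looks as far as week 91.
- **No comparison between phases is planned.** Correct. A reader might infer that the plan contains a confounded comparison of the extension with the blinded phase. It does not: section 7.2 gives descriptive percentages for each phase and no contrast between them. The risk lies in how the two tables are read.
- **Events may occur mainly during titration.** If so, length matters much less, as shown above. But section 1.5 names growth suppression and kidney stones, which need not be confined to the first weeks, and without exposure data the pattern cannot be seen.
- **A percentage is a valid description in so small a trial.** Agreed. This supports keeping it and adding exposure beside it. A rate per patient-year has its own weakness, because it assumes a roughly constant hazard.

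**Conclusion.** The concern holds for the extension part of the endpoint. Its percentage mixes risk with length of follow-up and should not be read against the blinded percentage. With extension lengths of 15 to 70 weeks, an unchanged risk could appear as 25% or 74% at an assumed constant 1 first event per patient-year, or as 13% or 49% at 0.5. These figures illustrate the possible size and do not predict it. They rest on assumed rates, a constant hazard, and whole cohorts placed at the ends of the range. The distortion in this trial depends on the spread of lengths that actually occurs and on when events happen.

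A reader might go further and conclude that the primary safety endpoint as a whole cannot be interpreted. The documents do not support that. The blinded percentages are reported by randomised arm under the same visit windows in both arms, and they remain interpretable. The extension percentage is itself a usable description once exposure is shown with it. This is an inexpensive improvement that should be made, not an error that undermines the trial's safety assessment.

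**What to change.** In section 7.2, Secondary Endpoint 1:

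1. Keep the planned percentages.
2. Define the extension denominator as patients who take at least one dose in the extension.
3. Summarise exposure time separately for the blinded and extension phases.
4. For each phase, add the cumulative incidence of the first related adverse event at a fixed time, for example 26 weeks from the start of that phase, with patients who leave earlier censored.
5. Add first events per patient-year with exact 95% confidence intervals, and note that this rate assumes a roughly constant hazard.
6. State that the extension and blinded percentages are not to be compared directly.

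Separately, reconcile the timings of Visit 5 and Visit 9 across the Study Summary and sections 3.3, 5.7.1, 6.5 and 6.9, so that the length of each phase has one definition.

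The cost is a few lines of text and one derived exposure variable, with no new visits or patients. The small downside is a few more descriptive figures with wide intervals at 26 to 33 patients.
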